7.8.2. Whole Blood Correlative Assessment

Whole blood samples will be used for immune cell population profiling (which may include T lymphocytes, B lymphocytes, myeloid, and natural killer cells). Other assays relevant to the objectives of the study, such as flow cytometry analysis of intracellular cytokines may be performed based upon emerging data.

7.8.3. Plasma Pharmacodynamic Assessment

Plasma samples will be evaluated to assess evidence of NC318 activity.

Plasma samples will be used to examine markers of inflammation or immune modulation (which may include, but are not limited to: IFN γ , IL-2, IL-4, IL-6, and TNF α) pre- and on-treatment with NC318. Other assays relevant to the objectives of the study may be performed based on emerging data.

7.8.4. Timing for Plasma and Whole Blood Assessments

Biomarkers will be analyzed in plasma and whole blood samples collected at baseline and on the days and times outlined in [Table 11](#). Timing for biomarker samples is outlined in [Table 11](#). Throughout the study, the exact date and time of the biomarker blood draws will be recorded in the eCRF along with the date and time study drug was administered in the clinic. For information regarding handling/shipping of specimens, please refer to the Laboratory Manual for the study.

7.9. Other Study Procedures

Not applicable.

8. SAFETY MONITORING AND REPORTING

8.1. Adverse Events

8.1.1. Definitions

For the purposes of this Protocol, an AE is defined as any untoward medical occurrence associated with the use of a drug in humans, whether considered drug related, that occurs after a subject provides informed consent and through the follow-up period.

Both nonserious and serious AEs (SAEs) will be monitored throughout the study.

A pre-treatment event (PTE) is one that occurs after the time of informed consent (e.g. during the screening process) but prior to study drug administration. PTEs directly related to a study test or procedure should be reported during the Screening period. Conditions that were already present at the time of informed consent should be recorded on the Medical History form in the eCRF.

A treatment-emergent adverse event (TEAE) is one that occurs from the time of the first dose of study drug through 90 days after the last dose of study drug. TEAEs should be monitored until they are resolved or are clearly determined to be due to a patient's stable or chronic condition or intercurrent illness(es).

Abnormal laboratory values or test results occurring after informed consent constitute AEs only if they induce clinical signs or symptoms, are considered clinically meaningful, require therapy (e.g., hematologic abnormality that requires transfusion), or require changes in the study drug(s).

8.1.2. Reporting

Adverse events monitoring will begin at the time the subject signs the ICF. All AEs and SAEs that occur after the consent form is signed but before first study treatment must be reported by the investigator **if** they are the result of a protocol-specified intervention.

From the time of first study treatment through 30 days following end of treatment, all adverse events must be reported by the investigator. SAEs will be collected for 90 days after the end of treatment or 30 days after the end of treatment if the subject initiates a new anticancer therapy.

AEs (including laboratory abnormalities that constitute AEs) should be described using a diagnosis whenever possible rather than by individual underlying signs and symptoms.

The severity of AEs will be assessed using NCI CTCAE v5.0 Grades 1 through 4. **The NCI CTCAE v5.0 severity of Grade 5 will not be used;** AEs resulting in death will be graded accordingly using Grades 1 through 4 and have the outcome noted as fatal.

If an event is not classified by NCI CTCAE v5.0, the severity of the AE will be graded according to [Table 13](#) to estimate the grade of severity.

Table 13: NCI CTCAE v5.0 Grading Scale

Grade	Clinical Characteristics
Grade 1	Mild; asymptomatic or mild symptoms; clinical or diagnostic observations only; intervention not indicated.
Grade 2	Moderate; minimal, local, or noninvasive intervention indicated; limiting age-appropriate activities of daily living.
Grade 3	Severe or medically significant but not immediately life-threatening; hospitalization or prolongation of hospitalization indicated; disabling; limiting self-care activities of daily living.
Grade 4	Life-threatening consequences: urgent intervention indicated.

The occurrence of AEs should be sought by nondirective questioning of the subject during the screening process after signing the ICF and at each visit during the study. Adverse events may also be detected when they are volunteered by the subject during the screening process or between visits, or through physical examination, laboratory test, or other assessments. To the extent possible, each AE should be evaluated to determine:

- The severity grade (NCI CTCAE Grade 1 to 4).
- Whether there is at least a reasonable possibility that the AE is related to the study treatment: suspected (yes) or not suspected (no).
- The start and end dates, unless unresolved at final follow-up.
- The action taken with regard to study drug.
- The event outcome (e.g., not recovered/not resolved, recovered/resolved, recovering/resolving, recovered/resolved with sequelae, fatal, unknown).
- The seriousness, as per SAE definition provided in [Section 8.3.1](#)

Unlike routine safety assessments, SAEs are monitored continuously and have special reporting requirements (see [Section 8.3.2](#)).

All AEs should be treated appropriately. If an AE is treated with a concomitant medication or nondrug therapy, this action should be recorded on the AE form in the eCRF and the treatment should be specified on the Prior/Concomitant Medications or Procedures and Non-Drug Therapy form in the eCRF.

Once an AE is detected, it should be followed until it has resolved or until it is judged to be permanent; assessment should be made at each visit (or more frequently if necessary) of any changes in severity, the suspected relationship to the study drug, the interventions required to treat the event, and the outcome.

When the severity of an AE changes over time for a reporting period (e.g., between visits), each change in severity will be reported as a separate AE until the event resolves. For example, 2 separate AEs will be reported if a subject has Grade 1 diarrhea, meeting the definition of an AE, that lasts for 3 days before worsening to a Grade 3 severity. The Grade 1 event will be reported as an AE with a start date equal to the day the event met the Grade 1 AE definition and a stop date equal to the day that the event increased in severity from Grade 1 to Grade 3. The Grade 3 event

will also be reported as an AE, with the start date equal to the day the event changed in intensity from Grade 1 to Grade 3 and a stop date equal to the day that the event either changed severity again or resolved.

8.2. Laboratory Test Abnormalities

Laboratory abnormalities that constitute an AE in their own right (considered clinically meaningful, induce clinical signs or symptoms, require concomitant therapy, or require changes in study drug) should be recorded on the AE form in the eCRF. Whenever possible, a diagnosis rather than a symptom should be provided (e.g., "anemia" instead of "low hemoglobin"). Laboratory abnormalities that meet the criteria for AEs should be followed until they have returned to normal or an adequate explanation of the abnormality is found. When an abnormal laboratory test result corresponds to a sign or symptom of a previously reported AE, it is not necessary to separately record the laboratory test result as an additional event.

Laboratory abnormalities that do not meet the definition of an AE should not be reported as AEs. A Grade 3 or 4 (severe) AE does not automatically indicate an SAE unless it meets the definition of serious, as defined in [Section 8.3.1](#). A dose modification for the laboratory abnormality may be required (see [Section 5.4.6](#)) and should not contribute to the designation of a laboratory test abnormality as an SAE.

8.3. Serious Adverse Events

8.3.1. Definitions

A serious adverse event (SAE) is defined as an event that meets at least 1 of the following criteria:

- Is fatal or life-threatening.
- Requires inpatient hospitalization or prolongation of existing hospitalization, unless hospitalization is a result of:
 - A routine treatment or monitoring of the studied indication not associated with any deterioration in condition.
 - An elective surgery or preplanned treatment for a pre-existing condition that is unrelated to the indication under study and has not worsened since signing the ICF.
 - A treatment on an emergency outpatient basis for an event not fulfilling any of the definitions of a SAE and not resulting in hospital admission.
 - Any social reasons and respite care, in the absence of any deterioration in the subject's general condition.
- Results in persistent or significant disability, incapacity, or a substantial disruption of a person's ability to conduct normal life functions.
- Constitutes a congenital anomaly or birth defect.
- Is an important medical event or a medically significant event that may not result in death, be immediately life-threatening, or require hospitalization but may be considered serious when, based on appropriate medical judgment, the event may jeopardize the subject or may require medical or surgical intervention to prevent 1 of the outcomes listed above.

Symptoms and clinical manifestations of disease progression can be classified as an SAE (if it meets the above criteria), however, progressive disease is not an SAE.

8.3.2. Reporting

Within 24 hours of identifying an SAE, regardless of the presumed relationship to the investigational product, the investigator or qualified designee must complete the SAE Report Form and submit it to the Sponsor or its designee. Instructions for SAE reporting will be provided by the CRO.

The sponsor is responsible for reporting certain SAEs as expedited safety reports to applicable regulatory authorities, ethics committees, and participating investigators, in accordance with ICH Guidelines and/or local regulatory requirements. The sponsor may be required to report certain SAEs to regulatory authorities within 7 calendar days of being notified about the event; therefore, it is important that investigators submit additional information requested by the sponsor or delegate as soon as it becomes available.

Investigators should provide all available information at the time of SAE Report Form completion. Investigators should not wait to collect additional information to fully document the event before notifying Sponsor or its designee of an SAE. When additional information becomes available, investigators should submit a follow-up SAE Report Form (separate from the initial report form) with the new information. Any follow-up information to an SAE also needs to be provided to Sponsor or its designee within 24 hours of learning of the new information.

8.3.3. Reporting of an Overdose

An overdose is defined as a subject receiving a dose of investigational product in excess of that specified in the Investigator's Brochure (IB), unless otherwise specified in this protocol.

Any overdose of a study subject with the investigational product, with or without associated AEs/SAEs, is required to be reported within 24 hours of knowledge of the event to Sponsor or its designee (see [Section 8.3.2](#) for contact information). If the overdose results in an AE, the AE must also be recorded on the AE eCRF. Overdose does not automatically make an AE serious, but if the consequences of the overdose are serious, for example death or hospitalization, the event is serious and must be reported as an SAE. NextCure does not recommend specific treatment for an overdose. The investigator will use clinical judgment to treat any overdose.

8.4. Emergency Unblinding of Treatment Assignment

Not applicable.

8.5. Pregnancy

Pregnancy, in and of itself, is not regarded as an AE unless there is suspicion that study drug may have interfered with the effectiveness of a contraceptive medication or method. When a pregnancy has been confirmed in a subject (or a male subject's partner) during maternal or paternal exposure to study drug, within 90 days of the last dose of study drug or within 30 days after cessation of treatment if the subject initiates new anticancer therapy, the following procedures should be followed to ensure subject safety:

- The study drug must be discontinued immediately (female subjects only).

- Consent must be obtained from female partners of male subjects.
- The investigator must complete and submit the NextCure Clinical Trial Pregnancy form to the sponsor or its designee within 24 hours of learning of the pregnancy.
- A serum pregnancy test must be performed to confirm the urine pregnancy test result (female subjects only).
- If a negative serum test does not confirm the urine pregnancy test result, then:
 - The investigator will use his or her expert judgment, based on an assessment of the potential benefit/risk to the subject, to determine whether it is in the subject's best interest to resume study drug and continue participation in the study.
- The EOT visit evaluations must be performed (female subjects only).

Data on fetal outcome and breastfeeding are collected for regulatory reporting and drug safety evaluation. Follow-up should be conducted for each pregnancy to determine outcome, including spontaneous or voluntary termination, details of the birth, and the presence or absence of any birth defects, congenital abnormalities, or maternal and/or newborn complications, by following until the first well-baby visit. Pregnancy should be recorded on a Clinical Trial Pregnancy form and reported by the investigator to the sponsor or its designee. Pregnancy follow-up information should be recorded on the same form and should include an assessment of the possible causal relationship to the sponsor's study drug to any pregnancy outcome. The baby should be evaluated for the first 8 weeks or the duration specified in local regulations, whichever is later.

Any SAE occurring during pregnancy must be recorded on the SAE report form and submitted to the sponsor or designee.

8.6. Warnings and Precautions

Special warnings or precautions for the study drug, derived from safety information collected by the sponsor or its designee, are presented in the IB. Additional safety information collected between IB updates will be communicated in the form of Investigator Notifications (INs). Any important new safety information should be discussed with the subject during the study, as necessary, and provided to the IRB. If new significant risks are identified, they will be added to the ICF.

8.7. Data Monitoring Committee

For Phase 1, the sponsor will conduct telephone conferences with investigators in order to review cohort-specific data, to review overall safety data from prior cohorts (if applicable), and to agree on dose escalation, de-escalation, and cohort expansion decisions on a regular basis.

For Phase 2, a formal DMC will be organized and comprised of the following members including but not limited to: a chairperson, two non-participating physicians specializing in oncology, the study medical monitor, a non-voting biostatistician, and representatives of the Sponsor and CRO. The committee will meet on a regular basis to review safety and tolerability throughout the study. Additional information on the DMC will be detailed in the DMC Charter.

8.8. Immune-Related Adverse Events

Adverse events of a potential immunologic etiology or irAEs may be defined as an AE consistent with an immune phenomenon associated with drug exposure after all other etiologies have been eliminated. Immune-related AEs may be expected based on the nature of NC318, its mechanism of action, and reported experience with other immunotherapies. Special attention should be paid to AEs that may be suggestive of potential irAEs. An irAE can occur shortly after the first dose or several months after the last dose of treatment. Guidance for the assessment, diagnosis, and management of irAEs is provided in [Section 5.4.7](#). Suspected irAEs should be discussed with the medical monitor.

Based on the known biology of the S15 pathway and its importance in immune function, as well as clinical experience with other immunotherapies in oncology, immune-related adverse events (irAEs) are the most likely class of toxicity.

9. STATISTICS

This section outlines the statistical analysis strategy and procedures for the study. If, after the study has begun, but prior to any final database lock, changes are made to primary and/or key secondary hypotheses, or the statistical methods related to those hypotheses, then the protocol will be amended (consistent with ICH Guideline E-9). Changes to exploratory or other non-confirmatory analyses made after the protocol has been finalized, but prior to final database lock, will be documented in a supplemental SAP (sSAP) and referenced in the Clinical Study Report (CSR) for the study. Post hoc exploratory analyses will be clearly identified in the CSR.

Tabular summaries will be presented by dose groups. Categorical data will be summarized by the number and percentage of subjects in each category. Continuous variables will be summarized by descriptive statistics including mean, standard deviation, median, minimal, and maximal values. All analyses, unless specified otherwise, will be based on as-treated population, which includes all subjects who receive any dose of NC318. Additional details of statistical analyses will be described in the SAP.

9.1. Study Populations

The full analysis set (FAS) includes all subjects enrolled in the study who received at least one full dose of NC318. This population will be used in all the summaries and analyses except for those of safety analysis set (SAS) and PK. The SAS will include all the subjects who receive any amount of study drug. The summaries and analyses of safety data will be performed on the SAS. The PK analysis set (PAS) will include all the subjects whose blood samples are collected for PK analysis. The PK data summaries and analyses will be performed on the PAS.

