5.4.8. Management of Infusion Reactions

Table 6 shows treatment guidelines for subjects who experience an infusion reaction associated with administration of study drug. Signs and symptoms usually develop during or shortly after drug infusion and generally resolve completely within 24 hours of completion of infusion. As of 29-SEP-2021 data cutoff, there were 4 with infusion reactions (two grade 1 [n=2] and two grade 2 [n=2]) amongst subjects from Phase 1 study (n=49) and 7 had infusion reactions (Grade 1 [n= 1], Grade 2 [n=5], and Grade 3 [n=1]) amongst subjects from Phase 2 study (n=43).

Table 6: Infusion Reaction Treatment Guidelines

NCI CTCAE v5.0 Grade/Severity	Treatment	Premedication at Subsequent Dose Administration
Grade 1: Mild reaction; infusion interruption not indicated; intervention not indicated.	Increase monitoring of vital signs as medically indicated until the subject is deemed medically stable in the opinion of the investigator.	None.
Grade 2: Requires therapy or infusion interruption but responds promptly to symptomatic treatment (e.g., antihistamines, NSAIDs, narcotics, IV fluids); prophylactic medications indicated for \leq 24 hours.	
Stop infusion and monitor symptoms. Additional appropriate medical therapy may include but is not limited to the following:
 
• IV fluids• Antihistamines• NSAIDs• Acetaminophen• Narcotics 
Increase monitoring of vital signs as medically indicated until the subject is deemed medically stable in the opinion of the investigator. If symptoms resolve within 1 hour of stopping drug infusion, the infusion may be restarted at 50% of the original infusion rate. Otherwise, dose administration will be interrupted until symptoms resolve, and the subject should be premedicated for the next scheduled dose. Subjects who develop Grade 2 toxicity despite adequate premedication should be permanently discontinued from further study drug administration.
	
Subject may be premedicated 1.5 h (\pm 30 min) prior to infusion with the following:
 
• Diphenhydramine 50 mg orally (or equivalent dose of antihistamine).• Acetaminophen 500-1000 mg orally (or equivalent dose of antipyretic).

NCI CTCAE v5.0 Grade/Severity	Treatment	Premedication at Subsequent Dose Administration

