9.5.4. Efficacy Analyses

The response will be assessed by CT/MRI image during screening and every 8 weeks (\pm 7 days) post-dosing for 6 months and then every 12 weeks (\pm 7 days) thereafter (or per standard of care). The efficacy study endpoints include ORR, DCR, DoR, PFS, and OS. Tumor response will be determined according to RECIST v1.1. Time-to-event data (DoR, PFS, and OS) will be analyzed using the Kaplan-Meier method. All the efficacy data will be summarized by phase, dose group, and cohort.

- ORR includes RECIST v1.1 complete and partial response (CR or PR). ORR with 95% exact CI will be summarized by phase, dose group, and cohort.
- DCR includes RECIST v1.1 complete, partial response, and stable disease (CR, PR or stable disease). DCR with 95% exact CI will be summarized by phase, dose group, and cohort.
- DoR is defined as the duration from the first documented ORR to the first documented progressive disease or death due to any cause, whichever occurs first. For subjects who are alive and progression-free at the time of discontinuation from study, data cutoff for analysis, or use of other anti-cancer drug, DoR will be censored at the last tumor assessment date.

The DoR will only be analyzed for the subgroup of subjects with an objective response.

DoR = (progressive disease, death, or censored date) – (date of first response + 1)

- PFS is defined as from starting study treatment to the first documented progressive disease or death due to any cause, whichever occurs first. For subjects who are alive and progression-free at the time of discontinuation from study, data cutoff for analysis, or use of other anti-cancer drug, DOR will be censored at the last tumor assessment date.

PFS = (progressive disease, death, or censored date) – (date of first dose of study drug + 1)

- OS is defined as from starting study treatment to death due to any cause. For subjects who are alive at the time of discontinuation from study or data cutoff for analysis, OS will be censored at the date of last known alive (LKA).

OS = (Death or LKA date) – (date of first dose of study drug + 1)

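### The efficacy analysis set requires one full dose, so subjects who never complete an infusion because of toxicity count for safety but leave the ORR and DCR denominators

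*Combined protocol and SAP*

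**What the plan says.** Three places bear on the efficacy denominator.

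- **Section 9 (opening text):** "All analyses, unless specified otherwise, will be based on as-treated population, which includes all subjects who receive any dose of NC318". Further detail is deferred to the SAP.
- **Section 9.1:** the FAS "includes all subjects enrolled in the study who received at least one full dose of NC318". On its use: "This population will be used in all the summaries and analyses except for those of safety analysis set (SAS) and PK". The safety set is wider: "The SAS will include all the subjects who receive any amount of study drug". The section does not define a full dose.
- **Section 9.5.4:** ORR, DCR, DoR, PFS and OS are defined without naming an analysis set. For response, "ORR with 95% exact CI will be summarized by phase, dose group, and cohort".

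Table 6 in Section 5.4.8 governs whether an infusion is completed. For a Grade 2 reaction: "Stop infusion and monitor symptoms". It continues: "If symptoms resolve within 1 hour of stopping drug infusion, the infusion may be restarted at 50% of the original infusion rate". If symptoms do not resolve in that time, dosing is interrupted and the subject is premedicated for the next scheduled dose. For Grade 3 or 4, the infusion is stopped and the subject receives no further drug.

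**The concern.** Completing an infusion happens after treatment starts and depends on how the drug is tolerated. Conditioning the efficacy set on it lets a drug effect decide who is counted. A subject with a Grade 3 or 4 reaction before any full dose can never enter the FAS. Neither can a subject with a Grade 2 reaction who completes no later infusion. Both stay in the safety set.

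These subjects have received almost no treatment and are expected to be failures. Removing them raises ORR and DCR. The study has no control arm, each expansion subgroup has at most 17 evaluable subjects, and ORR with an exact interval is a main efficacy summary. An avoidable choice that pushes the rate one way is therefore worth removing. Because Section 9 and Section 9.1 name different defaults, two statisticians could also report different denominators from the same data.

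**Working it through.** **1. Which set applies to efficacy.** Section 9 sets any dose as the default unless something else is specified. Section 9.1 specifies something else for all but safety and PK. Read together, efficacy falls on the full-dose FAS. On that reading the any-dose default governs almost nothing beyond safety, which the safety set already covers. Section 9.5.4 does not settle it.

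**2. Who is lost.** The FAS needs one full dose at any infusion, not a full first dose.

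| Situation | In safety set | In FAS |
|---|---|---|
| Grade 2, restarted and completed the same day | yes | yes |
| Grade 2, a later infusion completed | yes | yes |
| Grade 2, no infusion ever completed | yes | no |
| Grade 3 or 4 before any full dose | yes | no |
| Grade 3 or 4 after a full dose | yes | yes |

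**3. Reported reactions (Section 5.4.8, cutoff 29-SEP-2021).** The plan's totals reproduce.

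- Phase 1: 2 Grade 1 + 2 Grade 2 = 4 of 49.
- Phase 2: 1 Grade 1 + 5 Grade 2 + 1 Grade 3 = 7 of 43.
- Together: 11 of 92, of which 3 were Grade 1, 7 Grade 2 and 1 Grade 3.

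**4. Frequency of exclusion.**

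- Mandatory discontinuation (Grade 3 or 4): 1/92 = 1.1% (exact 95% CI 0.03 to 5.9%); Phase 2 only, 1/43 = 2.3% (0.06 to 12.3%). The documents do not say at which infusion it occurred or how much drug was given, so the number actually excluded could be 0 or 1.
- Extreme case, in which no subject with a Grade 2 or higher reaction ever completes a dose: (2 + 5 + 1)/92 = 8/92 = 8.7%; Phase 2 only, (5 + 1)/43 = 6/43 = 14.0%.

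Section 3.3.1 plans up to 85 expansion subjects (5 subgroups × 17).

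- If every mandatory-discontinuation reaction came before a full dose: 85 × 1/92 = 0.9 to 85 × 1/43 = 2.0 subjects.
- In the extreme case: 85 × 8/92 = 7.4 to 85 × 6/43 = 11.9 subjects.

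**5. Effect on ORR.** Let x be the responders, n the any-dose count and k the non-responders who never complete a dose. The any-dose rate is x/n and the FAS rate is x/(n − k). With x = 3:

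| Set-up | k | Any-dose | FAS |
|---|---|---|---|
| Lost subjects are additional to 17 | 1 | 3/18 = 16.7% (3.6 to 41.4) | 3/17 = 17.6% (3.8 to 43.4) |
| Lost subjects are additional to 17 | 2 | 3/19 = 15.8% (3.4 to 39.6) | 3/17 = 17.6% (3.8 to 43.4) |
| Lost subjects are among the 17 | 1 | 3/17 = 17.6% | 3/16 = 18.8% |
| Lost subjects are among the 17 | 2 | 3/17 = 17.6% | 3/15 = 20.0% |

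The first set-up applies if such subjects are replaced, the second if they are not. Either way one subject is worth about 1 point. Two per subgroup is roughly the Phase 2 extreme, since 17 × 6/43 = 2.4.

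**6. Data so far.** Section 1.3.4 reports 4 responders in 96 evaluable subjects. Dropping one non-responder moves 4/96 = 4.17% to 4/95 = 4.21%. The 96 equals the 49 + 47 enrolled in Section 3.3.1, so no exclusion is visible in that figure, although the section does not define evaluable.

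**The case against.** The case for leaving the text alone has several parts.

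- **A reader might infer that any stopped first infusion removes the subject.** The text does not support this. Table 6 lets a Grade 2 subject restart the same day or return premedicated, and weekly dosing for 8 cycles gives repeated chances to complete a dose. This stands.
- **A reader might infer that the two sections flatly contradict each other.** The default in Section 9 yields to anything specified elsewhere, and Section 9.1 can be that exception. It is an ambiguity about which set governs. This stands, but the full-dose condition remains under the most natural reading.
- **A reader might infer that the Simon decisions are distorted.** The stage rule in Section 9.2.2 asks whether there are 0 or at least 1 responses, and Section 9.2.2.1 and Section 3.1.2.2 count evaluable subjects. Section 9.2.1 defines evaluability only for DLTs. The rule does not use the FAS, so redefining the FAS does not directly change it. This stands.
- **A reader might infer that PFS and OS are biased upward too.** An infusion reaction is neither progression nor death, and Sections 6.4.1 and 7.6.1.4 keep following subjects who stop for other reasons. Excluding one could move either curve in either direction. DoR is confined to responders. This stands.
- **The effect is negligible beside the sampling error.** One point is small against an exact interval of 3.8 to 43.4% for 3/17, efficacy is secondary, and intolerance is fully reported in the safety set. The size is conceded. It does not justify keeping a condition that depends on tolerability when removing it costs only wording.

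**Conclusion.** The point holds for ORR and DCR. The FAS condition removes subjects who never complete an infusion because of toxicity while the safety set keeps them, and no section names a set for efficacy that would prevent it. The expected size is about 1 point of ORR per lost subject in a 17-subject subgroup, with perhaps 1 or 2 such subjects across the 85 planned.

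This rests on four assumptions:

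- The lost subjects are non-responders for ORR and not controlled for DCR. Removing such a subject can only raise the rate. A partly dosed subject with stable disease would be an exception for DCR.
- Reaction rates seen so far carry over to 800 mg weekly. The Phase 2 figures come from 400 mg every 2 weeks, and the Phase 1 figures from doses of 8 to 1600 mg.
- The one Grade 3 reaction may have preceded any full dose, which the documents do not state.
- The 8.7% and 14.0% figures require that no subject with a Grade 2 or higher reaction ever completed a dose. Nothing in the documents supports that. They mark the extreme for infusion reactions and are not an estimate.

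No effect on the Simon stage counts and no direction of bias in PFS or OS is claimed.

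**What to change.** 1. In Section 9.1, define the FAS as all enrolled subjects who received any amount of NC318. This matches the as-treated population in Section 9 and the safety set, and makes a definition of full dose unnecessary for this purpose.
2. In Section 9.5.4, name that set for ORR, DCR, PFS and OS. PFS and OS already start from the beginning of study treatment, which a partly infused subject has reached.
3. In Section 9.5.4, state that treated subjects without a post-baseline scan count as non-responders for ORR and as not controlled for DCR. Section 9.5.4 gives no such rule, and without it the same subjects could drop out by another route.

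The cost is wording. Sample size, visits, procedures and the stage rules do not change. The downside is that reported ORR and DCR may be slightly lower. The change should be made before the expansion results are reviewed.
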